85 study. Participants will receive a copy of the consent form prior to the first meeting so that they know from  
86 the onset what the study entails. Interested participants will be given an opportunity to ask any question  
87 over the phone or in the meeting before written informed consent is obtained. Consent will be only obtained  
88 once the participant has fully understood what the study entails and accept to take part in the study. If they  
89 decide to participate, they can withdraw from the research at any time and/or refuse to answer any questions,  
90 without suffering any negative consequences.

91 ***Eligibility***

92 To participate in this study, volunteers must be 60 or over 60 years old and able to understand  
93 instructions in English. We will not include people who a: present diagnosed psychiatric disorders or  
94 neurological pathologies (cardiovascular accidents, Parkinson’s or Alzheimer’s disease, dementia), b:  
95 unable to carry out the training program, or unable to understand the protocol, c: having motor deficit  
96 preventing physical activity without external help, d: having physical health status preventing physical  
97 activity and, e: alcohol or substance dependence.

98 ***Sample size***

99 Based on a meta-analysis reporting the effect size of interventions using the go/no-go task ( $g = .39$ )  
100 [32, 33], a desired statistical power of .9, and an alpha of .05 [34], a sample size calculation indicated that  
101 a minimum of 108 patients per condition is needed.

102 ***Ethics and dissemination***

103 This research will be performed in accordance with the Declaration of Helsinki. The study was  
104 approved by the University of Ottawa (Canada) Research Ethics Boards (H-09-22-8453). Potential  
105 participants will be informed of study details, including procedures, risks and benefits, confidentiality, and  
106 the voluntary nature of participation, before signing the consent form. Data will be kept on the uOttawa  
107 OneDrive, with access limited to team members. This system is protected by multi-factor authentication,  
108 meets Personal Health Information Protection Act requirements, and is serviced by the uOttawa

109 cybersecurity team. To guarantee that the research output is fully accessible to the public, the manuscripts  
110 will be published as preprints (e.g., SportRxiv) and data, material, and scripts will be made publicly and  

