140 of 400 trials for a total of 30 min. To assess the effect of the intervention, primary and secondary outcomes  
141 will be collected for one week, the week before the first session, the week following the last session of the  
142 intervention, as well as 1, 3, 6, and 12 months post intervention.

143

144 **Figure 3.** Protocol timeline.

145

146 ***Allocation and blinding***

147 Participants and research assistant will be blinded to the groups’ allocation. The participant blinding  
148 success will be appraised by asking them to guess in what group there were at the trial termination. Besides,  
149 the research assistant blinding success will be appraised via detecting the group allocation (Experimental  
150 vs. Control) by research assistant at the end of data collection phase. The randomization will be generated  
151 on a computer and an independent coworker will carry out the randomization. The participant’s  
152 identification number will be used to determine the sequence of randomization. Participants will be  
153 randomized in a 1:1 ratio between the intervention and active control condition.

154

155 ***Outcomes***

156 Participants will first respond to questions related to their age, sex (male, female), weight, and  
157 height.

158 ***Primary outcome***

159 The project focuses on device-based measures of physical activity and sedentary behaviors.  
160 Specifically, the primary outcomes collected using a physical-activity tracker will be the number of steps.  
161 Participants will be given the tracker and will be trained on how to wear the device (ie, over the right hip,  
162 affixed to an elastic belt, preferably worn under their waistbands). Currently, the waist based Actigraph is  
163 the most used device to objectively measure physical activity. Participants will be instructed to used it all

164 day long for 7 days and not to used it during shower or when they sleep at night. If the participant uses the  
165 tracker less than for 4 days in a row for at least 7 hours per day, they will not be included in the study. The  
166 number of steps measured in the week pre- and post-intervention, as well as 1, 3, 6, and 12 months after the  
167 intervention will be used as the primary outcome.

168 ***Secondary Outcomes***

169 The secondary outcomes will allow the examination of indirect health effects related to an increase  
170 in physical activity and a decrease in sedentary behavior.

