225 Statistical analyses will be performed according to the intention-to-treat principle and abide by the  
226 Consolidated Standards of Reporting Trials (CONSORT) guidelines. A sequential analysis will be  
227 conducted with an interim analysis after 50% of the data is collected and the other analyses after all data is  
228 collected [47]. Based on the Pocock boundary, the threshold for significant p-values will be .0294 [48]. If  
229 the effect is significant at the interim analysis, thereby indicating that the data provide support for the

230 hypothesis, data collection will be terminated. Mean, SD, median and range values will be used to  
231 summarize the continuous data. The primary outcome (number of steps per week) will be analyzed using  
232 multiple linear regressions. Particularly, we will test whether the participants' physical activity level  
233 (number of steps) the week after intervention termination will be higher in the intervention group relative  
234 to the control group, after adjustment for covariates (i.e., age, sex). Furthermore, we will test whether  
235 participants' automatic approach tendencies towards physical activity will be higher and participants'  
236 automatic approach tendencies towards sedentary behaviours will be lower in the intervention group  
237 compared to the control group.

238 *Secondary Analysis*

239 The continuous outcomes will be analyzed using linear mixed-effects models, which account for  
240 the nested structure of the data (i.e., multiple observations within a single participant), thereby providing  
241 accurate parameter estimates with acceptable type-I error rates [49]. To examine the effect of the  
242 intervention on the evolution of physical activity and sedentary behavior, models will include interaction  
243 terms between group (intervention group vs. comparison group) and number of days within or after (follow-  
244 up) the intervention. We will treat the continuous secondary outcomes in the similar way to the primary  
245 outcome. R software will be exploited for all analyses.

246 ***Data Monitoring***

247 The principal investigator will instruct all project team members to ensure that the study will be  
248 carried out according to the protocol. Research assistants will need to understand the protocol before  
249 starting the data collection. The ethics committee may visit the research sites for quality assurance. No  

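### The single-week primary regression has no analysis set or missing-data method, so it is complete-case by default, and it leaves out the pre-intervention step week that the trial collects

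*Combined protocol and SAP*

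**What the plan says.** Data analyses, Primary analysis, sets the principle: "Statistical analyses will be performed according to the intention-to-treat principle and abide by the" CONSORT guidelines. The same paragraph then defines the confirmatory test: "The primary outcome (number of steps per week) will be analyzed using" "multiple linear regressions. Particularly, we will test whether the participants' physical activity level" ("number of steps) the week after intervention termination will be higher in the intervention group relative") "to the control group, after adjustment for covariates (i.e., age, sex"). The outcome is therefore one week, and pre-intervention steps are not among the covariates.

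Four other places bear on this:

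- Primary outcome: steps are recorded before training, directly after it, and at 1, 3, 6 and 12 months. On short wear, the section says of a participant who uses the "tracker less than for 4 days in a row for at least 7 hours per day, they will not be included in the study". It does not say which measurement week this governs.
- Secondary Outcomes, Physical Functioning (a): self-reported moderate-to-vigorous physical activity (MVPA) from the IPAQ-SF is to serve as an adjustment variable. The primary analysis does not list it.
- Secondary Analysis: "The continuous outcomes will be analyzed using linear mixed-effects models, which account for" repeated observations on the same person. Models that can use partly observed participants appear only here.
- Recruitment: if participants "decide to participate, they can withdraw from the research at any time and/or refuse to answer any questions". Sample size gives no allowance for dropout.

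No section defines an analysis set, an imputation method, a missingness assumption or a sensitivity analysis.

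**The concern.** A linear regression cannot use a participant whose outcome is blank, and R's standard linear regression omits such rows by default. Someone who stops during the 12 training sessions, or who misses the post-training tracker week and returns at 1 month, would not contribute to the primary test, although other step weeks are on file for them.

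Leaving them out is harmless only if missing that week is unrelated to activity given arm, age and sex. Pre-intervention steps are the recorded variable most likely to predict both later steps and dropout, and the primary model does not contain them.

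Two things are at stake. One is possible bias in a result that would be reported as intention-to-treat. The other is precision lost whether or not there is bias. Because the handling of missing weeks is left open, it could also be chosen after data are seen, in a trial that may stop at an interim look at 50% of the data.

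**Working it through.** **The plan's own figures.** The standardised effect is .39 with 108 per condition (Sample size), and the threshold is .0294 (Primary analysis). The threshold reproduces: two Pocock looks at overall two-sided .05 give z = 2.178 and nominal p = .0294. The 108 does not reproduce at .39 (113 per arm one-sided, 139 two-sided). That is a separate matter and does not affect the bias figures below, so 108 is taken as given.

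**Assumptions, because the documents give none.** Step weeks have SD 1 and correlation .7. 10% or 20% miss the post-intervention week. Age and sex are unrelated to steps and to missingness. In the adverse scenario, the log-odds of missing fall by 0.7 per SD of pre-intervention steps in the intervention arm only (odds ratio exp(−0.7) = .50). In the control arm, missingness is unrelated to activity.

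**Why bias arises.** In this scenario,

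bias = correlation × (mean pre-intervention steps of intervention completers − that of control completers).

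The bracket is zero when the same mechanism acts in both arms. A bias of .05 SD means that completers differ at baseline by .05/.7 = .07 SD.

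**Simulated bias in SD units, 108 per arm.** Ranges reflect slightly different calibration of the missing rate.

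| Missingness and model | 10% missing | 20% missing |
|---|---|---|
| Intervention arm only; post week alone | +.045 to +.054 | +.09 to +.102 |
| Same mechanism in both arms; post week alone | about .00 | about .00 |
| Unrelated to activity; post week alone | about .00 | about .00 |
| Intervention arm only; complete-case regression with pre-intervention steps | about .00 | about .00 |
| Intervention arm only; mixed model on the step weeks | about .00 | about .00 |
| Depends on the unseen post-week steps, intervention arm only; adjusted for pre-intervention steps | about +.03 | about +.07 |

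With a true effect of .39, the post-week-only estimate averages .445 at 10% and .488 at 20%. The mixed model gives .390 and .386. At 5% missing, the one-arm mechanism gives only about +.025.

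Relative to the planned effect, .05/.39 = 13% and .10/.39 = 26%. With no true effect, a single two-sided look at .0294 rejects about 4.1% of the time at 10% missing and 6.1% at 20%.

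**A second route by hand.** Suppose that non-returners in both arms average 0.5 SD fewer steps than returners. Then bias = 0.5 × (difference in missing rates):

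- 20% against 10%: 0.5 × .10 = .05
- 30% against 10%: 0.5 × .20 = .10
- equal rates: 0

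**Precision.** Adjusting for a pre-intervention week with correlation r multiplies the standard error by about √(1 − r²). At r = .7 this is √.51 = .714, a cut of about 29% in large samples. The simulation gives about 27%, with differential missingness or without it. The formula gives 13% at r = .5, 20% at r = .6 and 40% at r = .8.

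**The case against.** A reader might infer that the plan specifies a complete-case test and so contradicts its own intention-to-treat statement. The documents do not support that. Nothing says that participants without the post week are dropped. Imputation before the regression would fit the text, the wear-time rule may concern only the baseline week, and analysing available outcomes by assigned arm is not incompatible with every use of the term. What stands is that the method is unspecified and its default is complete-case.

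A reader might also infer that the primary result will be biased. The bias needs activity-related dropout that differs between arms. Both arms receive identical instructions and the same task with only the stimulus proportions changed, and participants and the research assistant are blinded. Less active people leaving both arms alike is at least as natural, and the bias is then about zero. This objection stands, so the bias figures describe an adverse case and not an expectation.

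Third, the mixed model itself is not the main remedy. Complete-case regression with pre-intervention steps added removes the same bias. The mixed model's clean result also follows from letting missingness depend only on an observed variable. Both remarks are right.

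Finally, adjusting for MVPA might already help. It would, but little: a covariate correlated .3 to .5 with steps lowers the 20% figure only from about .09 to .07–.08 SD.

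**Conclusion.** The point holds as a gap with a better method readily available. It does not establish that the plan breaches intention-to-treat. The primary test has no stated analysis set or missing-data method, is complete-case by default, and discards the pre-intervention week.

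The possible bias is about +.05 SD at 10% missing and +.10 SD at 20%, against .39. This rests on one-arm activity-related missingness and a correlation of .7, neither of which the documents give; without a difference between arms it is about zero. The precision gain does not depend on that scenario: about 27% off the standard error at correlation .7, less if the correlation is lower.

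Two inconsistencies must be reconciled whatever the missing rate. The wear-time rule names no week, and it conflicts with intention-to-treat if applied after randomisation. MVPA is announced as an adjustment variable but is absent from the primary model.

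**What to change.** In the primary analysis section:

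1. Define the primary analysis set as all randomised participants in their assigned arm, and state the missing-data assumption.
2. Estimate the same contrast (group difference in the post-intervention week) from a linear mixed model with week as a category, using the pre-intervention week and all available follow-up step weeks, with age and sex as covariates. Regression adjusted for pre-intervention steps with multiple imputation would also serve.
3. Keep the ordinary regression as a sensitivity analysis.
4. Add one missing-not-at-random sensitivity analysis, for example lowering the imputed steps of withdrawn intervention participants until significance is lost. It is needed because the mixed model does not remove bias when missingness depends on the unobserved post-week steps.
5. State which week the wear-time rule governs and reconcile it with intention-to-treat.
6. State whether MVPA enters the primary model and, if so, from which time point.

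The cost is SAP wording and a little more R code. The data and the model class are already in the plan. The change should be made before the interim analysis.

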171 **1. Reflective and automatic processes underlying physical activity**

172 (a) *Explicit Affective Attitude Toward Physical Activity*: Explicit attitudes toward physical activity will  
173 be calculated as the mean of two items (Cronbach's alpha = 0.92) based on two bipolar semantic  
174 differential adjectives on a 7-point scale (unpleasant-pleasant; unenjoyable-enjoyable). The  
175 statement begins with "For me, to participate in regular physical activity is ..." [42].

176 (b) *Approach-avoidance task*: A contextual approach-avoidance task will be used to measure  
177 automatic approach and avoidance tendencies toward physical activity and sedentary behaviors  
178 [36]. Participants will be asked to move a manikin on the screen "toward" (approach condition)  
179 and "away" (avoidance condition) from images depicting physical activity and sedentary behaviors  
180 by pressing keys on a keyboard. Each trial will be started with a black fixation cross presented  
181 randomly for 250–750 ms in the center of the screen with a white background. Then, the manikin  
182 will be appeared in the upper or lower half of the screen. Concurrently, a stimulus depicting  
183 "movement and active lifestyle" (i.e., physical activity) or "rest and sedentary lifestyle" (i.e.,  
184 sedentary behavior) will be presented in the center of the screen. Participants quickly must move  
185 the human figure "toward" a stimulus (approach) depicting physical activity and "away" from a  
186 stimulus (avoidance) depicting sedentary behaviors, or vice versa. After seeing the manikin in its  
187 new position for 500 ms, the screen will be cleared. In case of an incorrect response, error feedback  
188 (i.e., a cross) will be appeared at the center of the screen.

189 **2. Physical Functioning**

190 (a) *Usual Level of Moderate-to-Vigorous Physical Activity*: The usual level of physical activity  
191 will be derived from the short form of the International Physical Activity Questionnaire  
192 (IPAQ-SF). The IPAQ-SF is a self-administered questionnaire that identifies the frequency  
193 and duration of moderate and vigorous physical activity, as well as sedentary time during the  
194 past 7 days to estimate usual practice of physical activity and sedentary behavior [46]. The  
195 usual level of moderate-to-vigorous physical activity (MVPA) in minutes per week will be  
196 used as a control variable in the analyses.

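### The primary regression adjusts for age and sex but leaves out pre-intervention steps, which the plan already records with the same tracker

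*Combined protocol and SAP*

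**What the plan says.** The Primary analysis section (under Data analyses) specifies a multiple linear regression of steps in the week after the intervention, comparing the groups "after adjustment for covariates (i.e., age, sex"). The list is introduced by i.e., so it reads as complete.

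The Experimental protocol section states that primary and secondary outcomes "will be collected for one week, the week before the first session", and again at the later visits. The Primary outcome section counts the "number of steps measured in the week pre- and post-intervention, as well as 1, 3, 6, and 12 months after the" intervention as the primary outcome, but the primary regression gives the pre-intervention week no role. That section also says that anyone who wears the "tracker less than for 4 days in a row for at least 7 hours per day" is not included. It does not say to which week this applies.

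Under Secondary Outcomes, item 2(a), MVPA from the IPAQ-SF questionnaire is to be "used as a control variable in the analyses". Neither the analyses nor the visit is named, and the Primary analysis section does not list it.

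For the longitudinal work, the Secondary Analysis section says: "The continuous outcomes will be analyzed using linear mixed-effects models". The time term counts days within or after the intervention, and pre-intervention steps are not given a role there either.

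**The concern.** A person's weekly step count before training is a natural predictor of the same count a few weeks later. Age and sex may carry little of that information. Leaving the baseline out puts predictable between-person variation into the residual, widens the confidence interval, and leaves a chance imbalance in baseline activity uncorrected. Randomisation still protects the estimate and the type I error, so only efficiency is at stake. The sample size section gives 108 per condition as a minimum and describes no allowance for dropout, so precision is not in surplus.

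The MVPA sentence adds a smaller problem. Two sections imply different covariate lists for the confirmatory model. A value collected after training could itself be affected by treatment, so the visit has to be stated.

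**Working it through.** **Inputs.** From the Sample size section: g = .39, power .90, alpha .05, 108 per condition. From the Primary analysis section: a nominal threshold of .0294, with an interim look at 50% of the data and a final look. Assumed, because the documents give no figure: r, the correlation of pre- and post-intervention weekly steps given age and sex, between .3 and .8. Also assumed: g is standardised on the unadjusted SD.

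**The plan's own figure.** With n per arm = 2(z_alpha + z_power)²/d²:
- one-sided .05, d = .39: 2(1.645 + 1.282)²/.1521, giving 113
- two-sided .05, d = .39: 2(1.960 + 1.282)²/.1521, giving 139
- one-sided .05, d = .40: 2(1.645 + 1.282)²/.16, giving 108

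The stated 108 is therefore not reproduced at .39. It matches a one-sided test with the effect rounded to .40. The text does not state sidedness, so both cases are shown below.

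**Gain from adjustment.** Residual variance is multiplied by 1 − r². The equivalent sample size is 108/(1 − r²) per arm and the effective effect is .39/√(1 − r²). At r = .5, variance is multiplied by .75, 108/.75 = 144, and .39/√.75 = .450.

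**Power.** For the two-look design the critical value is z(1 − .0147) at both looks. The test statistics have means d√(54/2) and d√(108/2) and correlation √.5. Under no effect the overall two-sided rejection rate is .050. The one-sided column is a single test at .05 (noncentral t, 214 df).

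| r | Variance reduction | Equivalent n per arm | Effective d | Power, two looks, two-sided .0294 | Power, single test, one-sided .05 |
|---|---|---|---|---|---|
| no baseline | – | 108 | .390 | .776 | .887 |
| .3 | 9% | 119 | .409 | .814 | .911 |
| .4 | 16% | 129 | .426 | .845 | .930 |
| .5 | 25% | 144 | .450 | .883 | .951 |
| .7 | 49% | 212 | .546 | .970 | .991 |
| .8 | 64% | 300 | .650 | .996 | .999 |

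A simulation of 8,000 two-look trials at r = .5 gave .770 unadjusted and .877 adjusted, in line with the table. The extra degree of freedom costs less than 0.01 percentage point of power.

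**Missing baselines.** If participants without baseline steps were deleted, and baselines were missing completely at random in a share m, relative information would be (1 − m)/(1 − r²). This equals 1 when m = r², so the gain is gone once 9% are missing at r = .3 (.09 × 216, about 19 people) or 25% at r = .5 (54 people). In a separate simulation at r = .5, with 10% of baselines missing and filled with the mean over both groups, power was .868 and null rejection .050.

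**The case against.** Four points can be made for the plan.

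1. **An activity covariate may already be in the model.** The MVPA sentence is not confined to secondary analyses, so on one reading the primary regression includes it and the gain is overstated. As an illustration, suppose pre-intervention MVPA correlates .3 with both pre- and post-intervention steps. The further variance reduction from adding steps is [(r − .09)/.91]²: about 5% at r = .3, 20% at r = .5 and 45% at r = .7, instead of 9%, 25% and 49%. Two-look power then goes from .814 to .835 at r = .3, and from .814 to .894 at r = .5. The gain shrinks, mainly at low r, but stays positive.
2. **The scale of g is not stated.** If .39 already refers to a baseline-adjusted SD, the adjusted powers are not additional to the plan. This stands as a limit on the power columns. It does not touch the variance reduction or the equivalent sample size, and on that reading omitting the baseline would leave power below the unadjusted figures in the table.
3. **r is unknown and may be low.** A record of as few as 4 days of 7 hours could be a noisy baseline. At r = .3 the gain is about 4 points of power with two looks and 2 points on the one-sided single test. This also stands.
4. **The wear rule may make baselines nearly complete.** If it is applied in the week before the first session, the deletion scenario hardly arises. A rule for missing baselines does no harm in that case.

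**Conclusion.** The concern holds. Pre-intervention steps are planned, are measured before training with the same device, and are absent from the primary covariate list. The defect is lost efficiency in a valid analysis. Its presence is clear from the text, but its size rests on the assumed r, and the power figures rest also on the assumed scale of g. The benefit could be modest or large, at almost no cost.

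The shortfall from the planned 90% to 78% comes from the sample size, the threshold and the choice of sidedness. It should not be attributed to this omission, although adjustment would recover part of it.

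**What to change.** - **Primary model.** In the Primary analysis section, specify post-intervention steps = group + pre-intervention-week steps + age + sex, and use the same model at the interim and final looks. Make the change before the interim analysis, so that covariates are not chosen with outcomes in view.
- **Missing baselines.** State that missing pre-intervention steps are replaced by the mean of observed values pooled over both groups, or handled with a missing indicator, so that no randomised participant is dropped for lacking a baseline.
- **MVPA.** Give one covariate list that agrees across Secondary Outcomes 2(a) and the Primary analysis section: either use only the pre-intervention MVPA value or drop MVPA.
- **Mixed models.** Say whether the pre-intervention value is a covariate or one of the repeated outcome observations. It should not be both.

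The cost is one degree of freedom for the added covariate and a few sentences of text. No new data are collected.
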